7.1.3 Pharmacogenetics analysis plan

This analysis will be performed at the end of the trial by Gateway Biotechnology. To identify genetic variants associated with ZNS protection against hearing loss, we will utilize genetic data collected from saliva samples to conduct a genetic association study. Variables including : sex, age, normalized values (Z-scores) of drug plasma concentration, Z-scores of noise intensity and duration, and Z-scores of hearing functions measured immediately following range shooting will be used in the analysis. Single-marker allelic association analyses will be conducted using PLINK v1.07. The data will be analyzed with a logistic regression model on the additive continuous dosage of minor alleles from 0 to 2 to account for uncertainty of imputation. We will combine association results in the two cohorts by performing a genome-wide inverse-variance weighting meta-analysis using PLINK v1.07, and assuming a fixed-effect model. Functional annotation of top-associated markers will be performed with R package NCBI2R 1.4.6 (<http://CRAN.Rproject.org/package=NCBI2R>), and key regional association plots of meta-analyzed results will be generated. To confirm whether these variants are specific to ZNS response, we will apply CEP SKAT to analyze genetic associations based on Z-scores of audiogram average threshold shifts and DPOAE amplitudes. All genetic variants, including both common and rare variants, will be included in this association study. Age, gender, drug concentration, and noise duration and intensity will be adjusted for the analysis. The analysis will also be performed using hearing data collected two to four weeks after range shooting. The only

differences will be a) using the Z scores of ECochG AP amplitude, latency, and width as well as WIN score, and b) using average audiogram threshold shifts and DPOAE amplitudes at 30 days (+/- 3 days) post-treatment. To control for confounding effects, these models will be adjusted for age, gender, and noise duration and intensity. Finally, the control and ZNS-treated comparisons will be performed using post-hoc comparisons with a Bonferroni adjustment for multiple comparison testing. Statistical analyses will be performed using the CEP-SKAT method in R language, and the statistical software SAS version 9.4 for Windows will be used for additional analysis.

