## **12.5 Pharmacogenetic analysis plan**

This analysis will be performed at the end of the trial by Gateway Biotechnology. To identify genetic variants with ZNS protection against hearing loss, we will first use univariate logistic regression analyses to identify potential confounding variables: sex, age, Z-scores of drug concentration, Z-scores of noise intensity and duration, and Z-scores of hearing functions measured immediately following range shooting. Single-marker allelic association analyses will be conducted on the two imputed data sets in PLINK v1.07. The data will be analyzed with a logistic regression model on the additive continuous dosage of minor alleles from 0 to 2 to account for uncertainty of imputation. We will combine association results in the two cohorts by performing a genome-wide inverse-variance weighting meta-analysis using PLINK v1.07, and assuming a fixed-effect model. Functional annotation of top-associated markers will be performed with R package NCBI2R 1.4.6 (<http://CRAN.Rproject.org/package=NCBI2R>), and key regional association plots of meta-analyzed results will be generated. To confirm whether these variants are specific to ZNS response, we will apply CEP SKAT to analyze genetic associations based on Z-scores of audiogram average threshold shifts and DPOAE amplitudes. All genetic variants, including both common and rare variants, will be included in this association study. Age, gender, drug concentration, and noise duration and intensity will be adjusted for the analysis. The analysis will also be performed using hearing data collected two to four weeks after range shooting. The only differences will be a) using the Z scores of ECochG AP amplitude, latency, and width as well as WIN score, and b) using average audiogram threshold shifts and DPOAE amplitudes at 30 days (+/- 3 days) post-treatment. To control for confounding effects, these models will be adjusted for age, gender, drug concentration, and noise duration and intensity. Finally, the control and ZNS-treated comparisons will be performed using post-hoc comparisons with a Bonferroni adjustment for multiple comparisons of any ZNS versus none.

Statistical analyses will be performed using the CEP-SKAT method in R language, and the statistical software SAS version 9.4 for Windows will be used for additional analysis.

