2.2.2 Secondary Objectives

To determine if ZNS is more effective than placebo in the prevention of additional auditory dysfunction in police officers following shooting range noise exposure as measured by ultra-high frequency audiometry, distortion product otoacoustic emissions (DPOAE), electrocochleography (EcochG) and words-in-noise (WIN) scores, and to determine a PGx link between NIHL and ZNS treatment effect.

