2.6 Schedule of Assessments and Procedures

The table below summarizes the calendar of study activities and assessments

	VISIT 1 Screening Assessment	VISIT 2 Baseline Assessment	Post-training		
			VISIT 3 Within 5-30 Minutes	VISIT 4 Within 24 Hours	VISIT 5 30 days (+/- 3 days)***
Informed Consent	X				
Demographic Info	X				
Current Meds	X				
Questionnaires	X				X
Cognitive Assessment		X		X	
Clinical ear exam	X	X	X		X
Audiogram	X	X	X		X
ECochG		X			X
DPOAE		X	X		X
WIN		X			X
Sound Measurements	X	X	X		X
Randomization			X*		

	VISIT 1 Screening Assessment	VISIT 2 Baseline Assessment	Post-training		
			VISIT 3 Within 5-30 Minutes	VISIT 4 Within 24 Hours	VISIT 5 30 days (+/- 3 days)***
Oral Dose* ZNS or Placebo			X*		
Blood draw**		X		X	
AE Assessment			X	X	X

* Dispensed after training if TTS is identified on audiogram 5-30 minutes after shooting.

** Blood draw: Electrolyte panel, BUN, Cr, ALT, and AST; DNA analysis and serum pregnancy test at baseline

***If TTS is seen from pure tones after each training session

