3.4 Exploratory analysis

Exploratory DNA analysis and phenotypic correlations with ZNS treatment.

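### The pharmacogenetic sections define no test of genotype by treatment: they pool an allele main effect over two undefined cohorts and adjust for a drug concentration with no listed assay

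*SAP*

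**What the plan says.** **Objective.** Protocol 2.2 and SAP 2.2.2 both include, among the secondary objectives, "to determine a PGx link between NIHL and ZNS treatment effect". SAP 3.4 places the same work in a lower tier: "Exploratory DNA analysis and phenotypic correlations with ZNS treatment".

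**Genetic model.** SAP 7.1.3 and Protocol 12.5 specify logistic regression on minor-allele dosage (0 to 2). The SAP continues: "We will combine association results in the two cohorts by performing a genome-wide inverse-variance weighting meta-analysis", under a fixed-effect model. The protocol has the same step ("We will combine association results in the two cohorts") and precedes it with "Single-marker allelic association analyses will be conducted on the two imputed data sets in PLINK v1.07".

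**Steps that mention ZNS.** A CEP-SKAT analysis of Z-scored threshold shifts and DPOAE amplitudes is meant to check that variants are specific to ZNS response. Post-hoc comparisons of control with ZNS, with a Bonferroni adjustment, close the section.

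**Drug concentration.** The SAP lists "normalized values (Z-scores) of drug plasma concentration" among its variables. Both documents adjust the CEP-SKAT analysis for concentration. For the models on 30-day data, the protocol keeps it as a covariate and the SAP omits it.

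**Samples.** The schedule footnote in SAP 2.6 (and Protocol 9.0) reads "Blood draw: Electrolyte panel, BUN, Cr, ALT, and AST; DNA analysis and serum pregnancy test at baseline". SAP 7.1.3 nevertheless relies on "genetic data collected from saliva samples".

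**The concern.** A genetic link to a treatment effect is effect modification: does the ZNS-placebo difference vary with genotype? An allele main effect answers another question, namely whether genotype predicts hearing loss whichever capsule was taken. If only the main effect is defined, the analyst must invent the test of the stated objective after the data are in, and a variant for noise susceptibility cannot be told from a variant for drug response.

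Two inputs also lack a source in the trial. The cohorts to be combined are not identified, and the concentration variable has no assay behind it. The two-cohort wording may be inherited: Protocol 1.4 says that methods from the investigators' study of age-related hearing loss will be reused here. The documents do not confirm this, and the point does not depend on it.

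**Working it through.** **1. Cohorts.** SAP 2.3 describes one population of officers randomised to two parallel groups. The only pair of groups in the trial is the pair of arms, so that is the reading tested below. On any other reading, the second cohort is not in the documents.

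**2. The figure that fixes N.** The documents give no power for the genetic analysis. The available N comes from SAP 2.7: 66 per arm, PTS 50% versus 25%, one-sided 0.025, 80.5% power. The Walters arcsine approximation to Fisher's test is

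power = Phi{ [asin sqrt(0.5 - 0.5/66) - asin sqrt(0.25 + 0.5/66)] x sqrt(132) - 1.960 } = 80.5%,

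which reproduces the plan. Exact enumeration of Fisher's test gives 81.3%.

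**3. What pooling the arms estimates.** Assume the outcome is PTS and the minor allele frequency (MAF) is 0.3; the documents do not give the MAF. In each arm the large-sample SE of the per-allele log OR is 1/sqrt[n p(1-p) x 2 MAF(1-MAF)], with 2 MAF(1-MAF) = 0.42.

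- Placebo: 1/sqrt(66 x 0.25 x 0.42) = 0.380
- ZNS: 1/sqrt(66 x 0.1875 x 0.42) = 0.439
- ZNS weight: (1/0.439²)/(1/0.439² + 1/0.380²) = 0.43

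For a variant that acts only under ZNS (OR 1/3 on ZNS, 1 on placebo), the pooled log OR is 0.4286 x ln(1/3) = -0.471, so OR 0.62. A prognostic variant with OR 0.62 in both arms gives the same pooled value.

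**4. Simulation.** 1,500 trials per scenario, 66 per arm, MAF 0.3, two-sided 0.05. Up to 7 trials per scenario were discarded because a fit failed or an SE was extreme.

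| Per-allele OR, placebo / ZNS | Mean pooled OR | Pooled test rejects | Interaction test rejects |
|---|---|---|---|
| 0.62 / 0.62 (prognostic only) | 0.62 | 32% | 4.5% |
| 1 / 0.33 (ZNS only) | 0.69 | 19% | 40% |
| 2 / 0.5 (opposite effects) | 1.16 | 3% | 61% |

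The ZNS-only mean is 0.69 rather than 0.62 because the weights are estimated in each trial. The pooled test rejects most often where there is no effect modification and least often where it is strongest.

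**5. Drug concentration.** The listed blood tests are electrolytes, BUN, creatinine, ALT, AST, a pregnancy test and DNA (Protocol 5.1, 5.4 and 9.0; SAP 2.6 and 8.2). No drug level is among them. Placebo officers would have a concentration of zero, so in a model on both arms the covariate would largely stand in for arm.

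**6. What an interaction could detect.** SE(interaction) = sqrt(SE placebo² + SE ZNS²). The detectable ratio of per-allele ORs is exp[SE x (1.960 + 0.842)] for two-sided 0.05 and 80% power.

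| Assumed MAF | SE(interaction) | Ratio at 0.05 | Ratio at an assumed 5e-8 |
|---|---|---|---|
| 0.1 | 0.886 | 12.0 | 264 |
| 0.2 | 0.665 | 6.4 | 66 |
| 0.3 | 0.580 | 5.1 | 39 |
| 0.5 | 0.532 | 4.4 | 28 |

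These are slightly optimistic. For a ratio of 3 at MAF 0.3 the formula gives Phi(1.099/0.580 - 1.960) = 47% power, against 40% simulated.

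**The case against.** The plan is not silent on drug response. It has a step aimed at ZNS specificity and a closing comparison of control with ZNS, and it nowhere says that main-effect findings will be reported as treatment modifiers. That is fair, so it would go too far to say that the objective cannot be met or that prognostic variants will be misreported. But neither step names an arm term, a contrast or, for the closing comparison, a phenotype. The gap remains.

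A reader might infer that every officer lacks the concentration value and that no part of the analysis can be run. The documents do not support this. The SAP's 30-day models already leave concentration out, and placebo concentration is zero by design rather than missing. Blood is also drawn 12 to 24 hours after dosing at Visit 4 (Protocol 5.4). What is missing is any listed assay.

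A reader might also infer that the two-to-four-week hearing data named in the section do not exist. Days 14 to 28 overlap the Visit 5 window (days 27 to 33) on days 27 and 28, and the next sentence of the section names 30 days (+/- 3). This is loose wording to tidy.

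Finally, SAP 3.4 already calls the DNA work exploratory, and no primary or interim decision depends on it. That limits the importance of the point but leaves the conflict with the secondary label in SAP 2.2.2 and Protocol 2.2.

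**Conclusion.** The point holds in this form: as specified, neither section contains a defined test of the pharmacogenetic objective. This rests on the text. The size of the problem rests on reading the cohorts as arms, on PTS as the outcome and on an assumed MAF of 0.3. On those assumptions, pooling gives the same large-sample OR (0.62) to a prognostic and a ZNS-only variant, and it flags opposite effects in 3% of trials where an interaction test flags 61%. If some other second cohort was meant, the documents do not identify it.

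The concentration variable has no listed source and would mostly duplicate arm. The two documents also disagree on whether it enters the 30-day models. The matter should be corrected before the genetic data are analysed; it does not touch the primary endpoint.

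**What to change.** Rewrite SAP 7.1.3 and Protocol 12.5 to match each other:

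- Remove the two-cohort meta-analysis and, in the protocol, the reference to two imputed data sets.
- Analyse the single randomised population. For each phenotype, fit treatment arm, genotype (or gene set) and genotype by arm, adjusted for age, sex, and noise duration and intensity. Make the interaction the result that answers the objective, and describe main effects as prognostic only.
- Delete drug concentration, since no assay is planned.
- State how many tests the Bonferroni adjustment covers.
- In the SAP, change the DNA source from saliva to blood, as in its own schedule.
- Align the two-to-four-week wording with the 30 (+/- 3) day visit.
- Call the analysis exploratory in Protocol 2.2 and SAP 2.2.2, in line with SAP 3.4.

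The cost is wording only, with no new sample or visit. The downside should be stated in the plan: with 66 officers per arm the interaction can detect only very large effects, and far larger ones still under a genome-wide threshold. A null result would therefore say little.

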2.7 Sample Size Determination for The Primary Efficacy Outcome Measure

Calculation of sample size for this study is based on a balanced design and a one-sided significance level of 0.025. We estimate that among officers identified as being at high risk for permanent hearing loss due to having TTS, the proportion of PTS positive officers 30 days (+/- 3 days) after shooting will be 50%. This is the proportion of PTS positive officers we expect to observe in the placebo group. Thus, for the primary outcome, we estimated that 66 officers per group will provide us with 80.5% power to detect a 50% reduction in the proportion of PTS positive officers (from 50% to 25%) at the 1-sided alpha level of 0.025. A planned total of 132 subjects is to be enrolled and randomized.

We will make all the needed efforts to eliminate drop outs, and due to short term-follow-up of the study subjects in a period we do not expect any drop-outs or lost to follow-up.

All sample size calculations were carried out using PROC POWER procedure in SAS 9.4.

3 Study Outcomes

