7.1.1 Analysis of primary outcome variable

Efficacy analysis at the end of the study

The primary outcome measure for assessing effectiveness of ZNS (100 mg PO) post-shooting compared to the placebo group will be the proportion of officers with TTS defined as PTS positive 30 days (+/- 3 days) after shooting range exposure.

Audiogram will be performed to look for PTS. Officers for whom the difference at any frequency from 2-6 kHz in hearing thresholds (30 days (+/- 3 days) post-shooting - Baseline) is ≥ 10 dB HL will be defined as PTS positive. Primary analysis and sensitivity analyses will be carried out on the primary endpoint.

Primary analysis

Frequency and relative frequency will be used to describe the distribution of the primary outcome measure in each study group. To assess efficacy, Fisher's exact test will be used to compare the proportion of officers with PTS positive in ZNS group with the proportion of officers with PTS positive in the placebo group.

The confidence intervals will be calculated using method 10 described by Newcombe RG, 1998 and also described by Altman et al.

1. Altman, Douglas, et al., eds. Statistics with confidence: confidence intervals and statistical guidelines. <https://www.amazon.com/Statistics-Confidence-Intervals-Statistical-Guidelines/dp/0727913751>

Let n_1 be the number of participants in placebo group, and r_1 the number of participants with PTS in the placebo group. $p_1=r_1/n_1$ be the proportion of PTS in the placebo group, and q_1 the proportion of participants that do not have PTS in placebo group.

l_1 and u_1 are the lower and upper limits of the $100(1-\alpha)\%$ confidence interval for p_1

Using Wilson method we calculate:

$$A_1 = 2r_1 + z^2$$

$$B_1 = z\sqrt{z^2 + 4r_1 q_1}$$

$$C_1 = 2(n_1 + z^2)$$

$$l_1 = \frac{(A_1 - B_1)}{C_1} \quad u_1 = \frac{(A_1 + B_1)}{C_1}$$

z_α = the $100(1 - \alpha)^{th}$ percentile of the standard Normal distribution.

Let n_2 be the number of participants in ZNS group, and r_2 the number of participants with PTS in the ZNS group. $p_2 = r_2/n_2$ be the proportion of PTS in the ZNS group, and q_2 the proportion of participants that do not have PTS in ZNS group.

l_2 and u_2 are the lower and upper limits of the $100(1-\alpha)\%$ confidence interval for p_2

$$A_2 = 2r_2 + z^2$$

$$B_2 = z\sqrt{z^2 + 4r_2q_2}$$

$$C_2 = 2(n_2 + z^2)$$

$$l_2 = \frac{(A_2 - B_2)}{C_2} \quad u_2 = \frac{(A_2 + B_2)}{C_2}$$

The proportion difference between groups is: $D = p_1 - p_2$

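### The pharmacogenetic confirmation step is not independent of the scan that picks the variants, so its false-confirmation rate can exceed nominal by an amount the plan leaves open

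*SAP*

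**What the plan says.** SAP 7.1.3, repeated almost word for word in Protocol 12.5, has two stages.

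- **Scan.** Single markers are tested genome-wide: "The data will be analyzed with a logistic regression model on the additive continuous dosage of minor alleles from 0 to 2". Results from two cohorts, never defined, are combined by fixed-effect meta-analysis. Then "Functional annotation of top-associated markers will be performed with R package NCBI2R 1.4.6".
- **Confirmation.** "To confirm whether these variants are specific to ZNS response, we will apply CEP SKAT to analyze genetic associations based on Z-scores" of average threshold shift and DPOAE amplitude. The analysis is repeated with later hearing data, including 30-day threshold shift and DPOAE.

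Neither section names the scan's binary outcome, the number of markers, the variant sets for SKAT, or the p-value that counts as confirmation. No hold-out sample, replication cohort or cross-validation is described. The only multiplicity rule is a Bonferroni adjustment for the closing comparison of control with ZNS.

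The DNA comes from the trial's own participants, and "A planned total of 132 subjects is to be enrolled and randomized" (SAP 2.7). SAP 2.2.2 makes it a secondary objective "to determine a PGx link between NIHL and ZNS treatment effect", as does Protocol 2.2. SAP 3.4 lists the DNA analysis as exploratory.

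**The concern.** A second test confirms a finding only if its null distribution still holds after the first test has been used to choose what is tested. Here the variants come forward because they separate hearing outcomes in these officers. They are then tested on related hearing outcomes in the same officers. The SKAT reference distribution assumes variants chosen without sight of those outcomes.

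Logistic regression needs a binary outcome, and the obvious candidate is PTS. SAP 3.2 defines PTS as a 30-day threshold shift of at least 10 dB, so it is a dichotomised relative of the second-stage phenotype. With no threshold on the scan, top markers exist even when no gene has any effect. At stake is whether a variant reported as confirmed means anything for the genetic objective.

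**Working it through.** **The plan's own figure.** The genetic sections state no power, error rate or threshold. The only related figure is the primary power, which fixes the sample size. "Calculation of sample size for this study is based on a balanced design and a one-sided significance level of 0.025", with 66 per group, 50% against 25%, and a stated 80.5%. SAP 7.1.1 specifies Fisher's exact test. Exact enumeration of the one-sided Fisher test gives 81.3%, within one point. The figure is reproduced, and N = 132 is taken from it.

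**Inputs.** From the documents: N = 132 and a pooled PTS rate of (50% + 25%)/2 = 37.5%. Assumed, because the documents give no values: PTS as the scan outcome, 50,000 to 1,000,000 independent common markers, the number carried forward, the correlation, and the p<0.05 bar.

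**Formula.** For a null marker with scan statistic z1, the second-stage statistic in the same officers is N(ρ·z1, 1 − ρ²), where ρ is the correlation between the binary outcome and the second phenotype. The chance of passing at p<0.05 is Φ((ρ·z1 − 1.96)/√(1 − ρ²)) plus a negligible opposite tail.

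Dichotomising at 37.5% gives ρ = 0.783 × r, where r is the latent correlation. At r = 0.7, ρ = 0.548. For the average of the top 10 of 100,000 null markers, z1 = 4.11, so (0.548 × 4.11 − 1.96)/√(1 − 0.548²) = 0.29/0.84 = 0.35, and Φ(0.35) = 64%. At ρ = 0 the chance is 5%.

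**Simulation with no genetic effect** (132 officers, 50,000 or 100,000 markers, top 20 retested singly, scan not adjusted for the second phenotype; three runs of 40, 60 and 120 replicates, the last column from the two 100,000-marker runs):

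| Latent r | ρ | Share of the 20 passing p<0.05 | At least one passing, Bonferroni over 20 |
|---|---|---|---|
| 0 | 0 | 5% | 7% |
| 0.3 | 0.23 | 13–18% | 17–19% |
| 0.5 | 0.39 | 30–33% | 58–67% |
| 0.7 | 0.55 | 58–60% | 91–97% |
| 0.85 | 0.67 | 74–82% | 100% |

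The r = 0 row comes from the 60-replicate run only. Using the ZNS arm alone (66 officers, 20 replicates) gives similar shares: 13%, 31%, 61% and 80%.

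**What lowers the rate.**

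- *Multi-variant sets.* With each top-10 marker placed in a 10-variant set of otherwise null variants, 9–13% pass at r = 0.5, 11–20% at 0.7 and 14–31% at 0.9.
- *A strict bar.* At an assumed gene-wide 2.5e-6, a top-ranked null marker passes at most about 4% of the time for ρ up to 0.7 with 500,000 markers (5.0% for the top one of 1,000,000). A 5e-8 threshold on the scan fired in at most 1% of null trials.
- *Adjustment.* If the scan includes the second-stage phenotype as a covariate, the pass rate is 5%, 5% and 7% at r = 0.5, 0.7 and 0.85, against 26%, 48% and 75% unadjusted in the same setting (30,000 markers, 40 replicates).

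**The case against.** The strongest objection is that the plan may not do what was simulated. Both sections say that all variants, common and rare, enter the association study, so CEP-SKAT is a scan in its own right and not a retest of 20 markers. It works on variant sets and extreme phenotypes, and no p<0.05 bar is stated. SAP 7.1.3 also lists hearing measured immediately after shooting among the variables to be used. If the first CEP-SKAT pass uses those same measures and the logistic scan adjusts for them, the inflation disappears. The DNA work is also labelled exploratory.

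Most of this stands, and it limits the size. It does not remove the dependence. Reading the scan's hits out of a wider CEP-SKAT run as confirmed still carries the selection. Protocol 12.5 treats the immediate measures only as potential confounders, so adjustment is not assured. In the 30-day repeat, no listed covariate is the 30-day phenotype itself, and the concern is clearest there. Pooling two undefined cohorts does not give replication. An exploratory label sits badly with a step described as confirmatory.

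A reader might go further and infer that chance variants would be confirmed almost every time. The documents do not support that. At least one of 20 uncorrected null tests reaches p<0.05 in 1 − 0.95^20 = 64% of trials with no selection at all, so a near-certain count of any hit is largely multiplicity. Per marker, near-certainty needs a high correlation, single-variant retests and a nominal bar together, and the plan states none of them.

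**Conclusion.** The point holds in a limited form. The second stage is not independent of the first and cannot confirm the selected variants at a nominal error rate, provided that the scan outcome is correlated with the second phenotype and the scan does not adjust for it. Under those conditions, the per-marker rate for single retests at p<0.05 runs from about 13% to about 82% over latent correlations of 0.3 to 0.85. It is lower for sets, small under a gene-wide threshold and about nominal with adjustment. The plan does not say which case applies.

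These figures rest on independent common markers, PTS as the scan outcome and modest replicate numbers, so they are approximate. It would also be too strong to infer that any positive genetic result is worthless: one passing a genome-wide threshold would still be informative. No primary efficacy conclusion depends on this step.

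**What to change.** In SAP 7.1.3 and Protocol 12.5:

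1. Delete the claim that CEP-SKAT in the same officers confirms the scan's hits. Name the scan outcome, its covariates, the two cohorts and the SKAT sets.
2. Declare a marker or gene associated only if it passes a prespecified threshold over everything tested, for example 5e-8 for single markers or Bonferroni over all gene sets.
3. For any follow-up test of scan-selected markers, take the p-value from permutation of the whole pipeline: permute phenotype and covariate records against genotype within treatment arm, and repeat both selection and test. A check with 3,000 markers, 99 permutations and 200 replicates at latent correlation 0.7 gave 6% false positives, consistent with 5%. Otherwise list the markers as hypothesis-generating and needing an independent sample, in line with SAP 3.4.
4. State that steps 2 and 3 guard against false association only. Specificity to ZNS, which is the stage's stated aim, needs a variant-by-treatment comparison.

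The cost is wording and computing time, with no added participants or samples. The downside is that few or no variants are likely to pass with 132 officers, so the genetic result becomes less favourable.
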